#### Exploratory Analyses

- Within-subject difference in diagnostic reasoning score between the 3 clinical vignettes without flawed LLM recommendations and 3 vignettes with flawed LLM recommendations and the corresponding difference in vignettes in the control group.
- Standalone LLM Performance: The standalone performance of the LLM will be compared to the control group using an independent samples t-test

Missing data patterns and extent will be described for all variables. The primary analysis will follow an intention-to-treat framework using complete case analysis. If substantial missing data occurs (>5% for any key variable), multiple imputation will be implemented and results compared with the complete case approach to assess robustness of findings. Given the small sample size, no interim analyses are planned.

All statistical analyses will be performed using Python software, version 3.11.12 (Python Software Foundation) with pandas for data manipulation and statsmodels version 0.14.4 for mixed-effects modeling, R (version 4.3.2 or later) or similar packages. Statistical significance will be based on a p value.

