#### Arms and Interventions

Arm	Intervention/Treatment
Active Comparator: ChatGPT-40	Other: ChatGPT-40 Recommendations with
Recommendations with Hallucinations	Hallucinations
Participants will evaluate six clinical vignettes.	
During the trial, they will have access to clinical	ChatGPT-40's differential diagnoses of six clinical
recommendations from a specific, commercially	vignettes, three of which will contain deliberately
available LLM (ChatGPT-40) in addition to	introduced inaccurate information.
conventional diagnostic resources. LLM	*
recommendations for three vignettes will contain	
deliberately flawed diagnostic information and for	
three vignettes it will contain accurate	
recommendations). The cases will be presented in	
random order.	
No Intervention: ChatGPT-40 Recommendations	
without Hallucinations	
Participants will evaluate the same six clinical	
vignettes as in the intervention arm. During the	
trial, they will have access to clinical	
recommendations from a specific, commercially	
available LLM (ChatGPT-40) in addition to	
conventional diagnostic resources. However, the	
LLM-generated recommendations will not contain	
any deliberately introduced errors. The cases will	
be presented in random order.	

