## **Outcome Measures**

#### **Primary Outcome Measures:**

*Diagnostic reasoning* [Time Frame: Assessed at a single time point for each case, during the scheduled diagnostic reasoning evaluation session, which takes place between 0-4 days after participant enrollment.]

The primary outcome will be the percent correct for each case, ranging from 0 to 100%, where higher scores indicate better diagnostic performance. For each case, participants will be asked for their three leading diagnoses, findings that support each diagnosis, and findings that oppose each diagnosis. For each plausible diagnosis, participants will receive 1 point. Findings supporting the diagnosis and findings opposing the diagnosis will also be graded based on correctness, with 1 point for each correct response. Participants will then be asked to name their top diagnosis they believe is most likely, earning 9 points for a reasonable response and 18 points for the most accurate response. Finally participants will be asked to name up to 3 next steps to further evaluate the patient with 0.5 point awarded for a partially correct response and 1 point for a completely correct response. The primary outcome will be compared at the case-level between the randomized groups.

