#### **Power Analysis:**

The minimum target sample size of 50 participants (25 participants per arm) was predetermined based on a prior study. The power analysis, conducted using Python version 3.11.9 (Python Software Foundation), employed the statsmodels.stats.power module from statsmodels version 0.14.4 (Statsmodels Developers) and indicated that a total sample of 200 to 250 completed cases (approximately 4 to 5 cases per participant) would provide at least 80% power to detect an 8-percentage-point mean difference in diagnostic reasoning scores, assuming a two-sided  $\alpha$  of .05. The analysis employed mixed-effects models suitable for cluster-randomized designs, considering an intraclass correlation coefficient (ICC) ranging from 0.05 to 0.15 and a standard deviation of 16.2%.

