The primary outcome analysis will be conducted at the case level, with clustering by participant under an intention-to-treat framework. The primary analysis will be based on cases with completed responses only. We will first summarize the mean and standard deviation of scores (standardized on a 0–100 scale) and report the mean and standard deviation for the time spent on each case, both for the overall cohort and separately for each of the study arms. To evaluate the impact of the treatment (i.e., providing access to recommendations some which contain inaccurate information), we will apply generalized mixed-effect models, including a random effect for the participant to account for potential within-participant correlation between cases, and a random effect for cases to account for differences in difficulty across cases. To improve precision, we will include the following covariates as control variables: past experience in LLM use, gender, and years of practice post MBBS. We will also conduct the following sensitivity analyses to assess the robustness of the findings:

- 1) Effect sizes without controls
- 2) The primary outcome analysis will be repeated including incomplete cases (if any) to evaluate the potential impact of missing data (e.g., using multiple imputation).
- 3) Inter-rater reliability for the diagnostic reasoning scores across at least two raters will be assessed using Cohen's kappa or Fleiss' kappa depending on the final number of raters.
- 4) The internal consistency of the diagnostic reasoning score across the six vignettes will be assessed using Cronbach's alpha.
- 5) Assessment of normality assumptions

For the secondary outcome (top choice diagnosis accuracy score), a mixed-effects ordinal logistic regression model will be used, with the same random effects structure as the primary analysis, and the dependent variable being the three-level final diagnosis accuracy (Incorrect, Partially Correct, Correct).

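### The exploratory LLM-versus-control t-test names no unit; on case scores it ignores shared vignettes and physician clustering, so its standard error is generally not valid (minor)

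*Combined protocol and SAP*

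**What the plan says.** Exploratory Analyses gives the comparison one line: "The standalone performance of the LLM will be compared to the control group using an independent samples t-test". It does not say whether a case score or a participant mean is the observation, how many LLM outputs per vignette are scored, or whether variances are pooled.

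Elsewhere the plan is specific about this score. Primary Outcome Measures says: "The primary outcome will be compared at the case-level between the randomized groups". The primary model in Statistical Analysis is described as "including a random effect for the participant to account for potential within-participant correlation between cases", and it also has "a random effect for cases to account for differences in difficulty across cases". In Arms and Interventions, the control arm's entry reads "Participants will evaluate the same six clinical" vignettes as the intervention arm, with LLM recommendations free of deliberate errors. The Power Analysis gives the variance inputs: "considering an intraclass correlation coefficient (ICC) ranging from 0.05 to 0.15 and a standard deviation of 16.2" percent.

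**The concern.** An independent samples t-test treats every observation as independent within and between groups. On case scores neither holds. Physicians and LLM are scored on the same six vignettes, so a hard vignette lowers both sides. Each physician also contributes up to six correlated scores. The plan models both features for the primary outcome and neither here.

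The two omissions pull in opposite directions. Vignette difficulty common to both sides cancels from a balanced difference but stays in the t-test's variance estimate, which inflates the standard error. Physician clustering is real variance that the t-test undercounts. What is at stake is one reported difference and its p value. A true LLM-physician gap could be missed, or, with many LLM runs pooled, a gap could be declared too readily. A reader could not tell which.

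**Working it through.** **Inputs from the documents.** 25 controls (target per arm), six shared vignettes, ICC 0.05-0.15, SD 16.2, two-sided alpha 0.05.

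**Assumed, because the documents do not give them.** Case-difficulty SD of 5, 10 or 15; LLM output SD of 3 to 16.2; number of LLM runs K. SD 16.2 is taken as the within-case SD, and LLM-by-vignette differences as zero unless stated.

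**The plan's own figure.** The only stated power is at least 80% for 8 points between the randomized arms. With design effect 1 + (m − 1) × ICC, 200 cases, m = 4 and ICC 0.15:
- design effect 1.45; effective n per arm 100/1.45 = 68.97
- SE = 16.2 × √(2/68.97) = 2.76; 8/2.76 = 2.90; power = Φ(2.90 − 1.96) = 82.6%

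The other corners are 90.3% (200 cases, ICC 0.05), 94.6% (250, 0.05) and 87.0% (250, 0.15). With 48 df the lowest is 81.1%. The figure reproduces and this point does not touch it. No power is stated for the LLM comparison.

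**Standard error of the case-level test.** Model: control score = case + participant + error (25 × 6 = 150 scores); LLM score = case + run noise (6K scores). Let S be the SD of the six case difficulties and Vp = ICC × 16.2² = 13.1 to 39.4. Residual and LLM noise are counted correctly, so

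E[Welch SE²] − true variance = S² × [5/(6(6K − 1)) + (125/149)/150] − Vp × [1/25 − (144/149)/150].

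The second bracket is 0.03356. For K = 1 the first is 0.17226, so at ICC 0.05 the terms balance at S = √(13.12 × 0.03356/0.17226) = 1.60. Break-even S:

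| K | ICC 0.05 | ICC 0.15 |
|---|---|---|
| 1 | 1.60 | 2.77 |
| 5 | 3.58 | 6.20 |
| 10 | 4.73 | 8.19 |
| 25 | 6.27 | 10.87 |

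Above the break-even the standard error is too large, below it too small.

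**One output per vignette, no true gap** (simulation, 20,000 replicates per cell, case difficulties drawn at random): pooled rejection 0-4.5%, Welch 0-5.0%.

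**One output per vignette, 10-point gap, LLM SD 10** (10,000 replicates):

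| Case SD | Case-level Welch | Vignette-paired |
|---|---|---|
| 5 | 42-43% | 43-45% |
| 10 | 26-27% | 44-46% |

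Holding the SD of the six difficulties exactly at 10, instead of drawing them, gives 23-24% against 44%.

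**25 runs pooled as independent, no true gap** (6,000 replicates, LLM SD 3 to 15): at ICC 0.15, 8.6-10.6% (case SD 5) and 5.9-7.1% (case SD 10); at ICC 0.05, 5.7-6.0% and 3.1-3.5%.

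**25 runs, inference beyond these six vignettes** (random LLM-by-vignette SD 5, LLM SD 10): case-level test 15.7-25.3%, participant means against run means 16.7-21.0%, vignette-paired 3.1-4.3%.

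**The case against.** The strongest reply is that the plan never says this test uses case scores. The case-level sentences concern the randomized groups and the primary analysis, and the LLM is not a randomized group. The neighbouring exploratory bullet is a within-subject difference, and other measures are computed per participant. Control participant means against LLM run means would be about right for these six vignettes. This stands as a limit: the invalid standard error belongs to the case-level reading, and what holds regardless is that the unit and runs are unstated. The case-level reading is still a natural one. No repeated runs are described, and a single run averaged over six vignettes leaves one LLM value with no within-group variance to test against.

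It is also fair that size and direction rest on assumed values, and that this is one exploratory line. Both are accepted. Three stronger readings are not supported:

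- **General false-positive inflation.** A reader might infer this. With one output per vignette, the Welch test is near nominal to conservative in the cells tried. The clear inflation arises with many pooled runs, which no section describes.
- **Large one-run errors from taking 16.2 as the total SD, case difficulty included.** At case SD 15 and ICC 0.15 this needs 15² + 0.15 × 16.2² = 264.4, more than 16.2² = 262.4, so the residual variance would be negative. No range that relies on that corner is used here.
- **Expected incomplete control data.** The Power Analysis mentions "a total sample of 200 to 250 completed cases (approximately 4 to 5 cases per participant"), and Statistical Analysis says "The primary analysis will be based on cases with completed responses only". The first is a count that suffices for power, not a forecast of yield; six vignettes are assigned to everyone.

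**Conclusion.** The point holds for a t-test on case scores: its standard error is generally not valid, and the documents do not fix the direction. With one LLM output per vignette the practical risk is lost power, from nothing material at case SD 5 to 26-27% against 44-46% at case SD 10. With 25 runs pooled as independent, false rejection is about 9-10.5% at ICC 0.15 and case SD 5, and about 3-7% in the other cells tried. It is higher if the LLM has vignette-specific strengths and inference is meant beyond these six. These sizes depend on the assumed case SD, LLM SD and number of runs, and are not estimates for this trial. Severity is minor: one exploratory difference and its p value are affected, and the primary and secondary results are not.

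**What to change.** Replace the t-test on case scores with a comparison balanced over the six vignettes.

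- **One output per vignette.** Use the vignette-paired difference, LLM score minus case-adjusted control mean, with SE² = (variance of the six differences)/6 + (participant variance)/(number of controls), on about 5 df.
- **Repeated runs, inference to these six vignettes.** Use the primary mixed model with fixed source, case and source-by-case effects, a participant random effect and a separate LLM residual variance, averaged over the six cases. With complete cases and at least about 5 runs, a Welch test of control participant means against LLM run means is enough.

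In either case state the unit, the number of runs, and whether the scored outputs are the ones shown to the control group. Report the difference with a 95% CI.

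The cost is SAP wording and a small calculation on existing data. Study Design gives completion as July 15, 2025, so a change after that date should be labelled post-completion. The one-run option has few df and a wide interval (half-width about 11 points at LLM SD 10), and no real power gain if the case SD is near 5. It also counts real LLM-by-vignette differences as error, so it is conservative for these six alone. With fixed differences of SD 5 and no average gap it rejects 2.7-3.5% at LLM SD 10 and 0.4-0.8% at LLM SD 3.

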This randomized controlled trial (RCT) aims to systematically measure the extent and patterns of automation bias among physicians when utilizing ChatGPT-40 in clinical decision-making. The investigators will assess how access to LLM-generated information influences diagnostic reasoning through a novel methodology that precisely quantifies automation bias. In this study, participants will be randomly assigned to one of two groups. The treatment group will receive LLM-generated recommendations containing deliberately introduced errors in a subset of cases, while the control group will receive LLM-generated recommendations without such deliberately introduced errors. Participants will evaluate six clinical vignettes randomly sequenced to prevent detection patterns. The flawed vignettes provided to the treatment group will incorporate subtle yet clinically significant errors that should be identifiable by trained doctors. This will enable investigators to quantify the degree of automation bias by measuring the differential in diagnostic accuracy scores between the treatment and control groups.

Prior to participation, all physicians will complete a comprehensive training program covering LLM capabilities, prompt engineering techniques, and output evaluation strategies. Responses will be evaluated by blinded reviewers using a validated assessment rubric specifically designed to detect uncritical acceptance of erroneous information, with greater score disparities indicating stronger automation bias. This naturalistic approach will yield insights directly applicable to real clinical workflows, where mounting cognitive demands may progressively impact diagnostic decision quality.

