## Study Design

Study Type: Interventional (Clinical Trial)

Actual Enrollment: 50 participants

Allocation: Randomized. Randomization list was created by [name] using the Sealed Envelope program.

Intervention Model: Parallel Assignment

Intervention Model Description: The trial will be designed as a randomized, two-arm, single-blind parallel group study.

Masking: Single (Outcomes Assessor)

Masking Description: The grading of responses will be performed by assessors blinded to participant identity and treatment assignment.

Primary Purpose: Diagnostic

Official Title: Trust or Verify? Automation Bias in Physician-LLM Diagnostic Reasoning

Actual Study Start Date: June 5, 2025

Actual Primary Completion Date: July 1, 2025

Actual Study Completion Date: July 15, 2025

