A secondary analysis will be conducted to measure the sequential trend in automation bias. A linear mixedeffects model will be used, with random intercepts for participants and for vignettes, and fixed effects for vignette order, treatment arm, and their interaction. The dependent variable will be the vignette-level diagnostic reasoning performance (percentage); the sequence-by-treatment interaction will then quantify how the treatment arm's trajectory deviates from control, reflecting any progressive automation bias across successive vignettes. We will repeat this analysis for the secondary outcome as well.

Subgroup analyses will be performed based on experience with LLMs, gender and years of practice post MBBS. Scores for each case question will also be compared descriptively between the two randomized groups.

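### The plan fixes neither the software nor the degrees of freedom behind the primary p value, and the default test of the tool it names is slightly anti-conservative with 50 participants

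*Combined protocol and SAP*

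**What the plan says.** The primary analysis is at case level. The Statistical Analysis section states that "we will apply generalized mixed-effect models, including a random effect for the participant", adds a random effect for case, and adjusts for three participant-level covariates: past LLM use, gender and years of practice. It then adds a linear mixed model for vignette order by arm, and says "Subgroup analyses will be performed based on experience with LLMs, gender and years of practice post" MBBS. It gives neither subgroup sizes nor the form of the subgroup model.

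The software paragraph at the end of Exploratory Analyses names "statsmodels version 0.14.4 for mixed-effects modeling" and, in the same sentence, allows R 4.3.2 or later or similar packages. Significance is to rest on a p value. No reference distribution, degrees-of-freedom method or small-sample correction is stated anywhere.

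On size, the Power Analysis gives a "minimum target sample size of 50 participants (25 participants per arm"), and the Study Design section records "Actual Enrollment: 50 participants".

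**The concern.** Arm is assigned to participants, so the arm effect is estimated from variation between 50 people, however many cases each completes. A test that treats the standard error as known is then somewhat too liberal. The linear mixed model in the named package does this by default: it reports z statistics and normal p values.

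Two things are at stake. The primary test can run above its nominal 5%. And because two engines are open, which may use different reference distributions, the choice between them could decide a borderline result.

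**Working it through.** **Inputs.** From the documents: 50 participants, 25 per arm; "a total sample of 200 to 250 completed cases (approximately 4 to 5 cases per participant"); six vignettes each ("Participants will evaluate six clinical vignettes randomly sequenced"); SD 16.2; ICC 0.05 to 0.15; two-sided alpha .05; three covariates. Assumed: one degree of freedom per covariate, and all subgroup sizes.

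**1. The plan's own power figure.** It claims "at least 80% power to detect an 8-percentage-point mean difference in diagnostic reasoning scores". With m cases per participant:

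- effective n per arm = 25m / (1 + (m − 1) × ICC)
- SE = 16.2 × √(2 / effective n)
- power = Φ(8/SE − 1.96)

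For the least favourable setting (m = 4, ICC 0.15), effective n = 100/1.45 = 68.97, SE = 2.759 and 8/2.759 = 2.900. Power is Φ(0.940) = 82.6%.

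| m | ICC | Power, z | Power, t on 48 df |
|---|---|---|---|
| 4 | 0.15 | 82.6% | 81.1% |
| 4 | 0.05 | 90.3% | 89.1% |
| 5 | 0.15 | 87.0% | 85.6% |
| 5 | 0.05 | 94.6% | 93.7% |

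The plan's figure reproduces, and it survives a t reference. On 45 df the lowest value is 81.0%.

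**2. Degrees of freedom for the arm effect.** 50 − 2 − 3 = 45 with covariates, and 50 − 2 = 48 without.

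**3. What the named tool reports.** In the installed version (0.14.6, not the plan's 0.14.4), MixedLM prints z and P>|z|, and its source has no Satterthwaite or Kenward-Roger option. Its residual df is the number of observations minus the rank of the fixed effects, about 295 with 300 rows and five fixed effects. Asking it for a t test therefore would not give about 45 df.

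**4. Size of the error, primary test.**

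- True size of a nominal 5% z test: 2 × P(t45 > 1.96) = 5.62%; on 48 df, 5.58%.
- Interval width: 2.014/1.960 = 1.028, so about 3% too narrow.
- Range of p that could change side: a z statistic of 2.014 has normal p = .044, so only z-based p values from about .044 to .050.

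Null simulation (20,000 trials per setting, balanced closed-form REML with participant variance truncated at zero, six cases each, ICC 0.05 to 0.15) gave 5.2% to 5.5% adjusted and 5.4% to 5.7% unadjusted. Most settings fall below the t calculation, as expected when truncation at zero inflates some standard errors at low ICC.

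**5. Subgroups, if each is fitted separately.** The documents give no sizes, so these are assumed.

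| Assumed size | df (n − 5) | z test by t theory | Simulated, ICC 0.05–0.15 |
|---|---|---|---|
| 12 per arm | 24 − 5 = 19 | 6.5% | about 5.3–6.4% |
| 6 per arm | 12 − 5 = 7 | 9.1% | about 5.6–7.9% |

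**6. Order-by-arm interaction.** With random intercepts only, this is a within-participant contrast. Its df is roughly 300 − 50 − 5 = 245, and 2 × P(t245 > 1.96) = 5.1%. The normal reference does no real harm there.

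**7. Crossed participant and case effects.** MixedLM is organised by group, but it can fit crossed effects by treating the whole data set as one group. In five simulated sets at ICC 0.10 the arm estimates equalled the closed-form REML answer, and standard errors agreed to about 0.4%, including in one fit flagged for non-convergence. In 100 simulated null trials with default settings and an assumed case SD of 5 or 10, 15 of 50 fits failed to converge at ICC 0.05 and 5 of 50 at ICC 0.15. A separate run at ICC 0.05 had 5 failures in 20.

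**The case against.** The strongest reply is that the plan does not commit to statsmodels. The sentence naming it also permits R or similar packages, so a reader who infers that the primary p value will be too small goes further than the text. That reply stands: the inflation is conditional on using the named tool with default output. What remains is that neither engine nor df method is fixed.

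Second, the primary effect is small. This also stands; it could matter only to a result very close to .05.

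Third, the subgroup figures rest on chosen sizes and on a separate model for each subgroup. An arm-by-subgroup interaction in the full model would keep all 50 participants. This stands, and the subgroup figures should be read only as a range under those assumptions.

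Fourth, a reader might conclude that statsmodels cannot fit the planned crossed model, or that every planned mixed model is affected. Neither is supported. The single-group route works and gives correct estimates, and the order-by-arm interaction is essentially untouched. What survives is practical: default convergence is unreliable at low ICC, which could force an unplanned change of engine, though another optimizer might rescue some of those fits.

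**Conclusion.** A minor but real point. The plan leaves open how the primary p value is obtained, and the default of the one tool it names for mixed models errs slightly in the liberal direction: about 5.2% to 5.7% against 5% for the primary test. The error becomes noticeable only in small subgroups fitted on their own. The documents do not support a stronger claim that the primary analysis is invalid, that the study is underpowered, or that the trial is bound to statsmodels.

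The figures assume normal, balanced and complete data, no arm-by-case variance, and one df per covariate. The package was checked in 0.14.6. The ordinal mixed model for the secondary outcome was not simulated, and nothing here applies to it.

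**What to change.** State in the software paragraph that the primary linear mixed model, and any linear mixed models for subgroups, are fitted in R with crossed random intercepts for participant and case, by REML. P values and 95% intervals should use Kenward-Roger or Satterthwaite degrees of freedom, with one of the two named in advance. Keep statsmodels as a cross-check only. The ordinal model for the secondary outcome is outside this change and needs its own statement of software.

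The Study Design section lists actual completion as July 15, 2025. If the analysis has already been run, the sentence can no longer pre-specify anything; report the df-corrected result beside the z-based one and say which software produced each.

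The cost is one sentence, in software already permitted, and primary intervals about 3% wider. There may also be some conservatism in very small subgroups at low ICC: t on between-participant df gave 2.6% to 3.9% with 12 participants in total, adjusted, at ICC 0.05 to 0.15. Kenward-Roger and Satterthwaite themselves were not simulated.
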